## Study Design

Prospective single center non-randomized clinical trial.

**Study Centers:** First Saint Petersburg State Medical University.

**Number of groups:** 3

Intervention:

Group 1: off-pump CABG

Group 2: on-pump CABG

Group 3: pump-assisted CABG (on-pump CABG without aortic cross-clamping)

**Sample size:** >300.

*Table 3 Number of patients*

Intervention	Number of patients	
	Planned	Actual
off-pump CABG	100	181 (175)
on-pump CABG	100	128 (127)
pump-assisted CABG	100	27 (33)
Total	300	336
Conversion	N/A	6

181 patient planned for elective CABG. There were 6 conversions to pump – assisted CABG (on-pump CABG without aortic cross-clamping). 175 received off-pump-CABG. 27 patient planned for elective pump – assisted CABG (on-pump CABG without aortic cross-clamping). 33 pump – assisted CABG were performed.

**Primary Endpoint:** MPO level after operation.

**Secondary Endpoints:** low output syndrome, length of stay in intensive care unit, length of stay in hospital, inotrope and vasopressor agents demand, duration of pulmonary ventilation, end systolic volume, end diastolic volume, ejection fraction, reoperation, renal dysfunction, atrial fibrillation, death during 30 days after CABG, stroke during 30-days after CABG.

Assessment of Myocardial Ischemic-Reperfusion Injury During Off- and On- Pump CABG (ClinicalTrials.gov Identifier: NCT03050489). Corresponding author: [name] [[contact]](mailto:[contact]) [contact]

Date of the document 06 December 2016

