# Assessment of Myocardial Ischemic-Reperfusion Injury During Off- and On- Pump CABG

(ClinicalTrials.gov Identifier: NCT03050489). Corresponding author: [name]

[[contact]](mailto:[contact]) [contact]

Date of the document 06 December 2016

- To compare inotrope and vasopressor agents demand after off-pump CABG, on-pump CABG and pump-assisted CABG (with cardiopulmonary bypass without aortic cross-clamping)
- To compare duration of pulmonary ventilation after off-pump CABG, on-pump CABG and pump-assisted CABG (with cardiopulmonary bypass without aortic cross-clamping)
- To compare end systolic volume, end diastolic volume, ejection fraction after off-pump CABG, on-pump CABG and pump-assisted CABG (with cardiopulmonary bypass without aortic cross-clamping)
- To investigate whether MPO level could predict outcomes after CABG
- To compare incidence of reoperation after off-pump CABG, on-pump CABG and pump-assisted CABG (with cardiopulmonary bypass without aortic cross-clamping)
- To compare incidence of renal dysfunction after off-pump CABG, on-pump CABG and pump-assisted CABG (with cardiopulmonary bypass without aortic cross-clamping)
- To compare incidence of atrial fibrillation after off-pump CABG, on-pump CABG and pump-assisted CABG (with cardiopulmonary bypass without aortic cross-clamping)
- To compare incidence of death during 30 days after off-pump CABG, on-pump CABG and pump-assisted CABG (with cardiopulmonary bypass without aortic cross-clamping)
- To compare incidence of stroke during 30-days after off-pump CABG, on-pump CABG and pump-assisted CABG (with cardiopulmonary bypass without aortic cross-clamping)

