#### **Exclusion criteria**

- Valve disease
- Acute coronary syndrome or urgent CABG

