#### **Myocardial Infarction 5 Type**

Myocardial Infarction 5 type defined as a troponin I elevation higher than 10 time 99th percentile URL with new Q-wave onset (ECG) or new regional wall motion abnormality (echocardiography) or graft/new coronary artery occlusion (angiography).

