#### **Baseline Characteristics**

**Hypothesis: baseline characteristics are comparable between groups.**

Hypothesis testing:

- Normality test (Kolmogorov-Smirnov test, Shapiro-Wilk test)

Assessment of Myocardial Ischemic-Reperfusion Injury During Off- and On- Pump CABG (ClinicalTrials.gov Identifier: NCT03050489). Corresponding author: [name] [[contact]](mailto:[contact]) [contact]

Date of the document 06 December 2016

Group comparing:

Continuous variables

- Non-normal distribution: Kruskal-Wallis test with adjustment for multiple comparisons
- Normal distribution: t-test with multiple comparison adjustment

Nominal variables

- Chi-squared test/ Fisher's exact test

Baseline characteristics:

*Table 4 Baseline characteristics specification*

Characteristic	Variable name in database	Test
Age	Age	t-test
Gender	Sex	Chi-squared test/ exact Fisher's test
Syntax Score I	SS1	Kruskal-Wallis test
Syntax Score II	SS2	Kruskal-Wallis test
Euroscore II	EII	Kruskal-Wallis test
Charlson/ Deyo Index	ICD	Kruskal-Wallis test
Ejection Fraction	EFPreOp	Kruskal-Wallis test
End diastolic volume	EDVPreOp	Kruskal-Wallis test
End systolic volume	ESVPreOp	Kruskal-Wallis test

*Table 5 Baseline characteristics*

Variables	off-pump CABG (N=181)	on-pump CABG (N=128)	pump-assisted CABG (N=27)	P Value
Age in years				0.7836*
Mean±SD	63.5±7.3	63.6±7.1	64.3±8.9	
Min–Max	43.0–79.0	33.0–80.0	46.0–80.0	
Median (IQR)	63.0 (59.0–68.0)	64.0 (59.0–68.0)	66.0 (58.0–69.0)	
Syntax Score I				0.3667**
Nmiss (%)	1 (0.6)	2 (1.6)	1 (3.7)	

Variables	off-pump CABG (N=181)	on-pump CABG (N=128)	pump-assisted CABG (N=27)	P Value
Mean±SD	26.2±9.4	27.4±7.7	27.8±6.7	
Min–Max	2.0–61.0	10.0–52.5	14.0–43.5	
Median (IQR)	24.4 (22.0–31.8)	25.8 (22.0–31.5)	27.0 (22.0–33.0)	
Syntax Score II				0.6002
Nmiss (%)	1 (0.6)	2 (1.6)	1 (3.7)	
Mean±SD	41.7±11.6	40.9±12.5	43.5±11.6	
Min–Max	8.1–68.0	3.7–68.3	24.6–67.6	
Median (IQR)	41.4 (32.7–50.8)	42.3 (31.1–49.9)	43.5 (34.5–53.6)	
EuroScore I				0.3137
Mean±SD	1.4±1.3	1.3±1.0	1.4±1.4	
Min–Max	0.5–10.8	0.5–5.5	0.5–6.7	
Median (IQR)	1.0 (0.7–1.5)	1.0 (0.6–1.5)	0.8 (0.6–1.4)	
Index Charlson/Deyo				0.1141
Nmiss (%)	1 (0.6)			
Mean±SD	5.4±2.0	5.0±1.8	4.9±2.0	
Min–Max	1.0–11.0	0.0–10.0	2.0–10.0	
Median (IQR)	5.0 (4.0–7.0)	5.0 (4.0–6.0)	5.0 (4.0–6.0)	
Ejection Fraction before operation				0.9090
Nmiss (%)	1 (0.6)	2 (1.6)		
Mean±SD	60.2±10.4	60.9±8.5	58.4±11.7	
Min–Max	30.0–85.0	28.0–85.0	30.0–72.0	

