### Secondary Endpoint Analysis

Hypothesis testing:

- Normality test (Kolmogorov-Smirnov test, Shapiro-Wilk test)

Group comparing:

Continuous variables

- Non-normal distribution: Kruskal-Wallis test with adjustment for multiple comparisons

*Table 29 Postoperative characteristics*

Variables	off-pump CABG (N=181)	on-pump CABG (N=128)	pump-assisted CABG (N=27)	P Value
ICU days				<.0001*
Mean±SD	2.5±2.2	3.1±3.1	3.3±1.9	
Min–Max	1.0–20.0	1.0–26.0	2.0–7.0	
Median (IQR)	2.0 (1.0–2.0)	2.0 (2.0–3.0)	2.0 (2.0–5.0)	
Days in hospital after CABG				0.0066*
Mean±SD	12.6±6.1	13.6±5.5	12.9±4.1	
Min–Max	0.0–50.0	0.0–33.0	3.0–25.0	
Median (IQR)	12.0 (10.0–13.0)	13.0 (11.0–15.0)	13.0 (10.0–15.0)	
Vasopressor and inotrope demand				0.0204*
Mean±SD	0.1±0.5	0.2±0.9	0.2±0.5	
Min–Max	0.0–4.2	0.0–8.4	0.0–2.1	
Median (IQR)	0.0 (0.0–0.1)	0.0 (0.0–0.1)	0.0 (0.0–0.1)	
Levosimendan demand				0.0220*
Mean±SD	0.0±0.1	0.2±1.8	0.7±3.8	
Min–Max	0.0–0.8	0.0–20.0	0.0–20.0	

Variables	off-pump CABG (N=181)	on-pump CABG (N=128)	pump-assisted CABG (N=27)	P Value
Median (IQR)	0.0 (0.0–0.0)	0.0 (0.0–0.0)	0.0 (0.0–0.0)	
Lenght of pulmonary ventilation				0.0181*
Mean±SD	1.2±1.2	1.5±1.6	1.4±0.7	
Min–Max	0.0–14.0	0.0–13.0	1.0–3.0	
Median (IQR)	1.0 (1.0–1.0)	1.0 (1.0–1.0)	1.0 (1.0–2.0)	
ESV after CABG				0.1283*
Nmiss (%)	22 (12.2)	22 (17.2)	3 (11.1)	
Mean±SD	42.7±23.5	45.2±21.0	50.9±32.2	
Min–Max	10.0–149.0	19.0–155.0	19.0–170.0	
Median (IQR)	37.0 (27.0–50.0)	40.5 (31.0–52.0)	40.5 (34.0–52.5)	
EDV after CABG				0.0508*
Nmiss (%)	22 (12.2)	22 (17.2)	3 (11.1)	
Mean±SD	103.7±37.7	107.2±32.6	122.3±40.4	
Min–Max	41.0–243.0	44.0–212.0	73.0–222.0	
Median (IQR)	97.0 (79.0–122.0)	106.0 (81.0–131.0)	109.5 (96.0–136.5)	
EF after CABG				0.9820*
Nmiss (%)	22 (12.2)	21 (16.4)	4 (14.8)	
Mean±SD	59.6±10.3	59.8±7.7	60.5±12.3	
Min–Max	29.0–86.0	28.0–73.0	23.0–88.0	
Median (IQR)	61.0 (54.0–66.0)	61.0 (58.0–65.0)	60.0 (55.0–67.0)	
End Systolic Volume				0.4178*
Nmiss (%)	5 (2.8)	5 (3.9)		
Mean±SD	48.0±28.0	46.8±23.0	50.5±20.7	
Min–Max	11.0–178.0	12.0–138.0	23.0–107.0	

Variables	off-pump CABG (N=181)	on-pump CABG (N=128)	pump-assisted CABG (N=27)	P Value
Median (IQR)	40.5 (31.0–55.0)	43.0 (32.0–54.0)	44.0 (38.0–55.0)	
Low Cardiac Output Syndrome				0.39 45*
No	166 (91.7)	113 (88.3)	26 (96.3)	
Yes	15 (8.3)	15 (11.7)	1 (3.7)	
Reoperation Cardio				0.83 61**
No	176 (97.2)	126 (98.4)	27 (100)	
Yes	5 (2.8)	2 (1.6)		

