Reoperation non cardio				0.07 40**
No	177 (97.8)	119 (93.0)	27 (100)	
Yes	4 (2.2)	9 (7.0)		
Kidney Damage				<.00 01**
Cr< URL	130 (71.8)	52 (40.6)	17 (63.0)	
Cr> 25% URL	49 (27.1)	70 (54.7)	7 (25.9)	
Hemodialysis				
2 (1.1)	6 (4.7)	3 (11.1)		
Atrial fibrillation				0.07 84**
No	155 (85.6)	101 (78.9)	19 (70.4)	
Yes	26 (14.4)	27 (21.1)	8 (29.6)	
Multiorgan dysfunction after CABG				0.00 17**
No	179 (98.9)	116 (90.6)	25 (92.6)	
Yes	2 (1.1)	12 (9.4)	2 (7.4)	
Infection or leukocytosis or febril >7 days				0.86 34**
No	166 (91.7)	117 (91.4)	26 (96.3)	
Yes	15 (8.3)	11 (8.6)	1 (3.7)	
Bleeding after CABG				0.00 14**
No	178 (98.3)	114 (89.1)	26 (96.3)	
Yes	3 (1.7)	14 (10.9)	1 (3.7)	
Graft thrombosis within 30d after CABG				0.82 95**
No	175 (96.7)	122 (95.3)	26 (96.3)	

Variables	off-pump CABG (N=181)	on-pump CABG (N=128)	pump-assisted CABG (N=27)	P Value
Yes	6 (3.3)	6 (4.7)	1 (3.7)	
Pulmonary dysfunction after CABG				0.04 92**
No	171 (94.5)	117 (91.4)	21 (80.8)	
Yes	10 (5.5)	11 (8.6)	5 (19.2)	
Neurological complications within 30d after CABG				0.03 22**
No	175 (96.7)	124 (96.9)	23 (85.2)	
Yes	6 (3.3)	3 (2.3)	3 (11.1)	
Death within 30d after CABG				0.25 45**
No	177 (97.8)	121 (94.5)	27 (100)	
Yes	4 (2.2)	7 (5.5)		
Intestinal complications within 30d after CABG				0.27 73**
No	180 (99.4)	127 (99.2)	26 (96.3)	
Yes	1 (0.6)	1 (0.8)	1 (3.7)	

\* Kruskal-Wallis test, \*\* exact Fisher's test. Nmiss – number of missing values, SD – standard deviation, IQR – interquartile range, CABG – coronary artery bypass grafting

Table 30 Troponin I level after CABG

Variables	off-pump CABG (N=181)	on-pump CABG (N=128)	pump-assisted CABG (N=27)	P Value
TnI before CABG				0.0938
Nmiss (%)	145 (80.1)	99 (77.3)	19 (70.4)	
Mean±SD	0.0±0.1	0.0±0.1	0.0±0.0	
Min–Max	0.0–0.5	0.0–0.2	0.0–0.1	
Median (IQR)	0.0 (0.0–0.0)	0.0 (0.0–0.0)	0.0 (0.0–0.1)	
TnI 1st day				<.0001
Nmiss (%)	17 (9.4)	10 (7.8)	1 (3.7)	
Mean±SD	2.5±8.9	6.0±10.3	4.7±7.3	
Min–Max	0.0–98.0	0.0–93.0	0.3–31.1	
Median (IQR)	0.4 (0.2–1.0)	3.1 (1.8–6.3)	1.4 (0.7–6.8)	
TnI 2st day				<.0001
Nmiss (%)	104 (57.5)	39 (30.5)	9 (33.3)	
Mean±SD	3.5±8.2	3.9±7.9	4.5±5.9	

Date of the document 06 December 2016

Variables	off-pump CABG (N=181)	on-pump CABG (N=128)	pump-assisted CABG (N=27)	P Value
Min–Max	0.0–50.0	0.0–50.0	0.2–18.8	
Median (IQR)	0.4 (0.2–2.1)	1.5 (0.7–3.4)	0.9 (0.4–6.1)	
TnI 3st day				0.1936

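### Atrial fibrillation is compared as an incidence over all patients, but prior AF is neither excluded nor reported, and the plan does not say how it is counted

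*Combined protocol and SAP*

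**What the plan says.** - **Endpoint.** Study Design lists AF among the secondary endpoints: "renal dysfunction, atrial fibrillation, death during 30 days after CABG". Secondary objectives gives the aim: "To compare incidence of atrial fibrillation after off-pump CABG, on-pump CABG and pump-assisted CABG".
- **Definition.** The Definitions section covers reperfusion injury and type 5 myocardial infarction, but not AF. Nothing limits AF to new onset.
- **Eligibility.** There are two exclusions: "Valve disease" and "Acute coronary syndrome or urgent CABG". Neither removes a patient with AF.
- **Baseline data.** Table 4 ("Baseline characteristics specification") lists age, sex, Syntax I and II, Euroscore II, Charlson/Deyo, ejection fraction and ventricular volumes. Rhythm and AF history are absent there and from Table 5.
- **Analysis.** Table 29 ("Postoperative characteristics") has a yes/no row labelled "Atrial fibrillation": 26 of 181 off-pump, 27 of 128 on-pump and 8 of 27 pump-assisted, with p = 0.0784 by Fisher's exact test.

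**The concern.** Incidence is the share of patients free of a condition at the start who then develop it. That requires knowing who was free of AF before surgery. The plan has no variable for this, and Table 29 removes nobody as not at risk.

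A patient with AF before surgery can distort the row in one of two ways. If recorded as an event, the patient inflates that technique's rate. If recorded as a non-event, the patient dilutes it. The documents do not say which was done.

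The groups were formed by department and lesion pattern, not at random. Balance in prior AF therefore cannot be assumed, and no table lets a reader check it. At stake is whether the row reports new AF after each technique or a mixture of new and old AF.

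**Working it through.** **Inputs** (Table 29): events 26, 27, 8; non-events 155, 101, 19; denominators 181, 128, 27. The number with prior AF is not given, so everything after step 1 is a scenario.

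**Step 1. Reproduce the printed figures.** 26/181 = 14.4%, 27/128 = 21.1%, 8/27 = 29.6%. The events total 61 and the patients 336. With all margins fixed, a table with a, b, c events has probability C(181,a)·C(128,b)·C(27,c)/C(336,61). Summing over all tables no more probable than the observed one gives p = 0.0784, as printed.

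**Step 2. One prior-AF patient, counted as an event, is removed from numerator and denominator.** Off-pump p = 0.059, on-pump 0.089, pump-assisted 0.132.

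**Step 3. Two such patients are removed, in every possible allocation.**

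| Off / on / assisted removed | Events / patients left | Exact p |
|---|---|---|
| 2 / 0 / 0 | 24/179, 27/128, 8/27 | 0.046 |
| 1 / 1 / 0 | 25/180, 26/127, 8/27 | 0.071 |
| 1 / 0 / 1 | 25/180, 27/128, 7/26 | 0.104 |
| 0 / 2 / 0 | 26/181, 25/126, 8/27 | 0.111 |
| 0 / 1 / 1 | 26/181, 26/127, 7/26 | 0.155 |
| 0 / 0 / 2 | 26/181, 27/128, 6/25 | 0.195 |

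One allocation of the six falls below 0.05, and four move p further above it. If the two were a random pair of the 61, the chance that both were off-pump would be (26 × 25)/(61 × 60) = 17.8%.

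**Step 4. Assume equal prior-AF prevalence in all groups,** rounded to whole patients. The two columns take the two possible counting rules.

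| Assumed prevalence (patients removed) | p if all were counted as events | p if all were counted as non-events |
|---|---|---|
| 2% (4, 3, 1) | 0.079 | 0.070 |
| 3% (5, 4, 1) | 0.070 | 0.068 |
| 5% (9, 6, 1) | 0.027 | 0.086 |
| 8% (14, 10, 2) | 0.017 | 0.077 |

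At 5%, the at-risk rates would be 17/172 = 9.9%, 21/122 = 17.2% and 7/26 = 26.9% if the removed patients had been events. They would be 26/172 = 15.1%, 27/122 = 22.1% and 8/26 = 30.8% if they had been non-events. The counting rule matters more than the small change in denominator.

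**The case against.** **The documents never say that existing AF was counted as an event.** This is correct. A reader might infer it from the missing definition and the full denominators, but no text states such a rule. Some wording leans the other way: the objective speaks of incidence after surgery, and the Adverse Events section limits an adverse event to something new or to a worsening of an existing condition. That section does not govern the endpoints by name, so the question stays open. Even if only new AF was recorded, patients with prior AF would still be in the denominator.

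**Table 29 is headed as postoperative.** This settles little. The table also contains an End Systolic Volume row identical to the pre-operative row in Table 5 (48.0, 46.8 and 50.5, p = 0.4178). A patient in permanent AF is also still in AF after surgery. Equally, the lack of an after-surgery suffix on the AF label proves nothing, since six other complication rows lack one too, including both reoperation rows.

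**The p-value shift has little decision weight.** This stands. A reader might infer that any two prior-AF patients would carry the result past 0.05, but that happens only if both were off-pump. No alpha is stated, Sample Size Justification calls the study exploratory, and AF is one of 13 listed secondary endpoints.

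**The row is confounded anyway.** This also stands: allocation was by clinical choice and the comparison is unadjusted. Restricting it to new AF does not cure that.

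**Rhythm may have been recorded.** It may have been. Tables 4 and 5 show only that it was not specified or reported as a baseline characteristic.

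**Conclusion.** The point holds as a gap between the stated objective and the specified analysis. The plan promises an incidence, but neither identifies the patients at risk nor restricts the analysis to them. The printed 14.4%, 21.1% and 29.6% therefore cannot be confirmed as incidence. If no patient had prior AF, they are correct as they stand.

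The size of any error is unknown. Under the scenarios above, p moves in either direction from 0.0784: between 0.046 and 0.195 for two removed events, and down to 0.017 at an assumed 8% prevalence with all such patients counted as events. These figures rest on assumed counts and an assumed counting rule, and 0.05 is a yardstick that the plan does not set. They show that the row is sensitive to missing information, not that it is wrong in a particular direction.

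This is a worthwhile improvement to one secondary endpoint. The primary MPO comparison is not affected.

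**What to change.** 1. Take AF history and pre-operative rhythm from existing records. The type 5 infarction definition asks for a Q wave that is new, which implies an earlier ECG for comparison, so the data are probably available.
2. Add AF before surgery, by group, to Tables 4 and 5.
3. Define the endpoint as new AF within 30 days of surgery in patients without prior AF.
4. Rerun the AF row on that denominator with the same exact test. Keep the all-patient row as a supplement, with a note on how prior AF was counted.
5. State beside the row that the comparison remains unadjusted and the groups non-randomised.

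The cost is some chart review, one more baseline variable, one rerun test and a slightly smaller denominator. If the review finds no prior AF, the present row stands and one sentence is enough to say so.

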[[contact]](mailto:[contact]) [contact]

Date of the document 06 December 2016

Type of trial	Prospective non-randomised single-centre
Type of research	Exploratory
Timeline	2015-2019
Groups	Off-pump  On – pump  Pump-assisted (on-pump without aortic cross-clamping)
Sample size estimation	> 300 patients
Planned sample size	Average: 300  Off-pump: 100  On-pump: 100  Pump-assisted: 100
Actual sample size	Average: 336  Off-pump: 181 (conversion 6)  On-pump: 128  Pump-assisted: 27
Baseline characteristics comparing	Testing for type of distribution of baseline characteristics:  ANOVA for normal distribution  Kruskal-Wallis test with multiple groups comparison adjustment for non-normal distribution  Chi-squared test or exact Fisher's test for nominal data
Statistics hypothesis testing	ANOVA/ANCOVA for MPO level, troponin I level
Missing Data Handling	Drop observations with missing data
Evaluating of reason of missingness	Hypothesis: Missing data depend on severity of complications  Hypothesis testing with logistic regression model: Missingness = complications

Assessment of Myocardial Ischemic-Reperfusion Injury During Off- and On- Pump CABG  
(ClinicalTrials.gov Identifier: NCT03050489). Corresponding author: [name]  
[[contact]](mailto:[contact]) [contact]

Date of the document 06 December 2016

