### **Primary objective**

- To compare MPO level before and just after performing coronary anastomosis during off-pump CABG, on-pump CABG and pump-assisted CABG (with cardiopulmonary bypass without aortic cross-clamping)
- To compare TnI level between groups

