Nmiss (%)	149 (82.3)	90 (70.3)	21 (77.8)	
Mean±SD	3.4±7.4	2.5±2.8	4.8±4.5	
Min–Max	0.1–40.7	0.1–14.6	0.5–10.9	
Median (IQR)	1.1 (0.2–3.5)	1.4 (0.6–3.5)	2.6 (1.9–10.0)	
TnI 4st day				0.3843
Nmiss (%)	168 (92.8)	108 (84.4)	22 (81.5)	
Mean±SD	5.4±7.5	2.3±3.0	2.7±3.2	
Min–Max	0.0–27.9	0.1–10.7	0.2–8.3	
Median (IQR)	3.2 (1.3–7.5)	0.9 (0.4–2.6)	1.5 (1.4–2.0)	
TnI 5st day				0.2222
Nmiss (%)	158 (87.3)	106 (82.8)	23 (85.2)	
Mean±SD	1.5±2.1	0.9±1.4	2.4±1.9	
Min–Max	0.0–6.6	0.0–5.9	0.5–4.9	
Median (IQR)	0.3 (0.0–2.5)	0.4 (0.1–0.8)	2.2 (1.2–3.7)	

Table 30 Troponin I level after CABG in patients without low cardiac output syndrome after CABG

Variables	off-pump CABG (N=166)	on-pump CABG (N=113)	pump-assisted CABG (N=26)	P Value
MPO before operation				0.3871
Nmiss (%)	27 (16.3)	18 (15.9)	9 (34.6)	
Mean±SD	36.0±32.6	38.8±29.5	29.0±15.3	
Min–Max	2.8–237.8	4.1–168.9	5.6–65.4	
Median (IQR)	28.1 (16.4–40.6)	30.8 (19.3–47.7)	28.7 (18.7–34.0)	
MPO after operation				0.3871
Nmiss (%)	27 (16.3)	18 (15.9)	9 (34.6)	
Mean±SD	36.0±32.6	38.8±29.5	29.0±15.3	
Min–Max	2.8–237.8	4.1–168.9	5.6–65.4	
Median (IQR)	28.1 (16.4–40.6)	30.8 (19.3–47.7)	28.7 (18.7–34.0)	
TnI before CABG				0.0403

Date of the document 06 December 2016

Variables	off-pump CABG (N=181)	on-pump CABG (N=128)	pump-assisted CABG (N=27)	P Value
Nmiss (%)	134 (80.7)	89 (78.8)	18 (69.2)	
Mean±SD	0.0±0.1	0.0±0.1	0.0±0.0	
Min–Max	0.0–0.5	0.0–0.2	0.0–0.1	
Median (IQR)	0.0 (0.0–0.0)	0.0 (0.0–0.0)	0.0 (0.0–0.1)	
TnI 1st day				<.0001
Nmiss (%)	14 (8.4)	8 (7.1)	1 (3.8)	
Mean±SD	1.1±2.6	4.1±4.0	4.1±7.0	
Min–Max	0.0–18.5	0.0–18.7	0.3–31.1	
Median (IQR)	0.4 (0.2–0.7)	2.5 (1.7–5.0)	1.4 (0.7–2.7)	
TnI 2st day				<.0001
Nmiss (%)	100 (60.2)	37 (32.7)	9 (34.6)	
Mean±SD	1.9±4.7	2.3±3.0	3.9±5.5	
Min–Max	0.0–29.8	0.0–15.0	0.2–18.8	
Median (IQR)	0.3 (0.1–1.0)	1.2 (0.6–2.5)	0.9 (0.4–5.9)	
TnI 3st day				0.0828
Nmiss (%)	140 (84.3)	84 (74.3)	21 (80.8)	
Mean±SD	1.4±2.0	1.8±1.8	3.5±3.7	
Min–Max	0.1–9.2	0.1–6.5	0.5–10.0	
Median (IQR)	0.6 (0.2–2.1)	1.1 (0.5–2.9)	2.3 (1.9–3.0)	
TnI 4st day				0.6389
Nmiss (%)	158 (95.2)	99 (87.6)	21 (80.8)	
Mean±SD	2.6±3.1	2.0±2.7	2.7±3.2	
Min–Max	0.0–9.1	0.1–8.3	0.2–8.3	
Median (IQR)	1.6 (0.3–4.1)	0.8 (0.4–2.6)	1.5 (1.4–2.0)	
TnI 5st day				0.0541
Nmiss (%)	149 (89.8)	96 (85.0)	22 (84.6)	
Mean±SD	0.8±1.6	0.7±1.0	2.4±1.9	
Min–Max	0.0–5.8	0.0–3.8	0.5–4.9	
Median (IQR)	0.1 (0.0–0.9)	0.3 (0.1–0.8)	2.2 (1.2–3.7)	

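### Day-2 troponin was measured in 42.5% of off-pump but 69.5% of on-pump patients, so the complete-case day-2 comparison is at high risk of selection bias, probably but not demonstrably towards understating the difference in means

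*Combined protocol and SAP*

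**What the plan says.** The Primary objective section lists, beside the myeloperoxidase (MPO) comparison, "To compare TnI level between groups". Under Missing Data Handling, the statistical synopsis (Table 2) gives the rule "Drop observations with missing data". For non-normal data, the Secondary Endpoint Analysis section specifies the Kruskal-Wallis test.

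Table 30 heads its columns with the full arms (181, 128, 27). For day 2 it gives these missing counts: "104 (57.5) 39 (30.5) 9 (33.3". The measured patients have mean±SD "3.5±8.2 3.9±7.9 4.5±5.9" and median (IQR) "0.4 (0.2–2.1) 1.5 (0.7–3.4) 0.9 (0.4–6.1", with p<.0001. For day 1 the missing counts are "17 (9.4) 10 (7.8) 1 (3.7" and the means "2.5±8.9 6.0±10.3 4.7±7.3".

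The second table numbered 30 covers patients without low output syndrome (166, 113, 26) and gives day-2 missing counts "100 (60.2) 37 (32.7) 9 (34.6". Table 31, for patients with the syndrome (15, 15, 1), gives 4, 2 and none.

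The section on the mechanism of missingness models only post-operative MPO. No day-2 TnI sampling rule, reason for missing TnI or sensitivity analysis for it is stated.

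**The concern.** On day 1 nearly everyone was sampled, at similar rates in each arm. On day 2 most on-pump patients were sampled and most off-pump patients were not. If the off-pump patients who had a second sample were those who gave cause for worry, the complete-case rule compares a higher-troponin selection from one arm with something closer to a full arm from the other.

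This touches the trial's own question, because the Introduction names troponin dynamics after different types of CABG as the gap in evidence. The on/off ratio of printed means falls from 6.0/2.5 = 2.4 on day 1 to 3.9/3.5 = 1.1 on day 2. From the tables alone a reader cannot separate change in injury from change in who was sampled.

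**Working it through.** **Coverage (N minus missing, over N).**

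| | Off-pump | On-pump | Pump-assisted |
|---|---|---|---|
| Day 1 | 164/181 = 90.6% | 118/128 = 92.2% | 26/27 = 96.3% |
| Day 2 | 77/181 = 42.5% | 89/128 = 69.5% | 18/27 = 66.7% |
| Day 2, no low output | 66/166 = 39.8% | 76/113 = 67.3% | 17/26 = 65.4% |
| Day 2, low output | 11/15 = 73.3% | 13/15 = 86.7% | 1/1 |

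The strata add to the totals: 100+4 = 104, 37+2 = 39, 9+0 = 9. Off-pump against on-pump on day 2, Fisher's exact p is about 3e-6 overall and 1e-5 without low output syndrome. The syndrome does not explain the gap.

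**Reproducing the printed day-2 means** from the stratum means (without the syndrome 1.9 and 2.3; with it 13.1 and 13.4):
- Off-pump: (66×1.9 + 11×13.1)/77 = 3.50 (printed 3.5)
- On-pump: (76×2.3 + 13×13.4)/89 = 3.92 (printed 3.9)

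The difference is 0.42. Its standard error is √(8.2²/77 + 7.9²/89) = 1.25.

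**Over-representation of low output syndrome among those measured.** Off-pump: 11/77 = 14.3%, against 15/181 = 8.3% of the arm. On-pump: 13/89 = 14.6%, against 15/128 = 11.7%.

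**Standardising to each arm's own low-output share**, which assumes that sampling within arm and stratum is unrelated to TnI:
- Off-pump: (166×1.9 + 15×13.1)/181 = 2.83
- On-pump: (113×2.3 + 15×13.4)/128 = 3.60

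The difference is 0.77 (0.67 to 0.87 over rounding of the inputs).

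**Relaxing that assumption, with the same rule in both arms.** Let the unmeasured patients without the syndrome average between the measured median and mean: 0.3 to 1.9 off-pump (x), 1.2 to 2.3 on-pump (y). Low-output patients keep their measured mean.
- Off-pump: (66×1.9 + 100x + 15×13.1)/181 = 1.94 to 2.83
- On-pump: (76×2.3 + 37y + 15×13.4)/128 = 3.28 to 3.60

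The difference runs from 3.283 − 2.828 = 0.45 to 3.601 − 1.944 = 1.66, and the ratio from 1.16 to 1.85.

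**Is the direction fixed?** A full-arm mean equals the measured mean minus the missing share times the gap (measured minus unmeasured mean). The printed difference understates the true one only if 0.575 × off-pump gap exceeds 0.305 × on-pump gap. For a positive off-pump gap, this means an on-pump gap below 1.89 times the off-pump gap. The documents report neither gap. Extreme settings for the unmeasured without the syndrome give −0.15 (off-pump at 1.25 times the measured mean, on-pump at zero) to 1.73 (off-pump at 0.25 times, on-pump at 1.25 times).

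**Day 1 to day 2 by stratum (means).** With low output syndrome: off-pump 20.0 to 13.1, on-pump 21.0 to 13.4. Without it: on-pump 4.1 to 2.3, off-pump 1.1 to 1.9. Of these four cells, only the least-sampled one rises. Had that stratum's true mean stayed at 1.1 (an assumption), its unmeasured patients would average (166×1.1 − 66×1.9)/100 = 0.57, against 1.9 in those measured.

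**The case against.** A reader might infer from the coverage gap that the day-2 comparison is biased and understates the off-pump versus on-pump difference. The documents do not support that as a statement of fact. Unequal coverage establishes neither bias nor its direction, and no table splits day-1 TnI by whether a day-2 sample was taken. The Patients allocation section sends every Department #1 patient to off-pump surgery, so part of the gap could be departmental routine unrelated to TnI. The documents do not say.

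The rise in the off-pump mean without low output syndrome is also fragile. The median in the same rows falls from 0.4 to 0.3. The day-2 maximum is 29.8 against 18.5 on day 1; without that single value the mean is (1.9×66 − 29.8)/65 = 1.47, so it supplies about half of the 0.8 rise. The on-pump fall may be ordinary kinetics.

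The printed test does not compare means, either. The section specifies a rank test, the measured medians differ about fourfold (0.4 against 1.5; 0.3 against 1.2 without the syndrome), and p<.0001 in both tables. Nor does the document claim that off-pump injury catches up with on-pump; its troponin summaries concern day 1 only. The study calls itself exploratory, and its primary endpoint is MPO.

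All of this stands against a claim of proven bias or a wrong direction of effect. It does not remove the risk. With 104 of 181 off-pump values missing, the measured values do not bound that arm's full-cohort median. The plan examines missingness for MPO but not for TnI, although TnI is part of the primary objective. The reversal at −0.15 is possible arithmetically but strained: it needs every unmeasured on-pump patient without the syndrome to average zero, when the measured lower quartile is 0.6.

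**Conclusion.** The coverage gap is exact, is not explained by low output syndrome, and is not addressed in the plan. The complete-case day-2 comparison is at high risk of selection bias. Understatement of the difference in means is the more plausible direction, because low-output patients are over-represented among those measured, more so off-pump, but it is not shown.

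The size is modest and uncertain. The difference moves from 0.42 to 0.77 if sampling is unrelated to TnI within arm and low-output stratum, and lies between 0.45 and 1.66 under the symmetric median-to-mean assumption. The lower end is close to the printed figure, and the shift to 0.77 is small against a standard error of about 1.25. The finding that on-pump TnI is higher is unlikely to change. The day-1 comparison, with even coverage and medians of 0.4 against 3.1, does not share the problem.

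**What to change.** 1. Name day-1 TnI as the between-technique TnI comparison for the primary objective.
2. For day 2, base inference on a mixed model of log TnI on days 1 and 2 (technique, day, technique × day; unstructured covariance; a small stated offset for zeros), using every patient with either value. Report day-2 estimates with intervals. The Kruskal-Wallis p-value can stay beside it, labelled complete-case and descriptive.
3. Tabulate day-1 TnI in patients with and without a day-2 sample, by arm. This tests the direction of selection directly.
4. Add a sensitivity analysis weighting measured patients by the inverse probability of day-2 sampling, given technique, day-1 TnI and low output syndrome.
5. State that the change in raw means from day 1 to day 2 is not to be interpreted as a difference in troponin dynamics between techniques.

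The cost is SAP wording and a few analyses of data already collected, with no new samples. Because the document already prints results, these analyses should be marked as added afterwards. The downside is the assumption that day-2 sampling depends only on technique, day-1 TnI and, in the weighted analysis, recorded low output status. Sampling prompted by something else on day 2 would not be corrected.
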